#### **5.1 ALL ENROLLED**

This analysis set will include patients who have been enrolled in THAOS study and have signed the informed consent form.

The enrollment date will be considered as the date when informed consent form (ICF) was signed.

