## 5.3 TAFAMIDIS TREATED

The tafamidis treated set will include the following:

[figure not shown]
- All available data from the enrollment date until final treatment discontinuation of tafamidis or end of follow-up in THAOS (whichever is earlier) for patients who have been enrolled in THAOS, signed the informed consent and who were on tafamidis treatment on or prior to the date of enrollment in THAOS.
- All available data from first dose of tafamidis until final treatment discontinuation of tafamidis or end of follow-up in THAOS (whichever is earlier) for patients who were not on tafamidis at the time of enrollment in THAOS but subsequently initiated treatment with tafamidis.

Note: A patient can be considered part of both the tafamidis untreated and tafamidis treated sets if the patient initiated treatment with tafamidis after beginning participation in THAOS.

The below schematic will help to better understand the patient population to be analysed:

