**\*Changes of phenotype**

Under the assumption that phenotype-related symptoms do not truly disappear, but are only possibly masked or temporarily resolved, once determined, phenotype classification

PFIZER CONFIDENTIAL

will be carried forward to future visits even if there are no available symptom data at the subsequent visit. Patients classified as predominantly cardiac or predominantly neurologic at a given visit will continue to be classified as such at subsequent visits unless the patient develops additional symptoms warranting a re-classification to mixed phenotype. Missing data on prior visit will disqualify re-classification (participant must have data entered in the same measure to allow comparison and reclassification). The mixed phenotype is a persistent state, i.e, once a patient is classified as mixed phenotype at a given visit, then that patients remains mixed at all subsequent visits.

For those patients who initiated treatment with tafamidis after beginning participation in THAOS, phenotype treatment baseline will be the most recent phenotype classification prior to first dose.

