#### **6.2.1 Survival**

Survival will be analysed as time from enrollment or first dose of tafamidis, for the untreated and tafamidis treated set respective until the time of death. Patients who are still alive at the end of the analysis period (start of tafamidis or end of follow-up in THAOS for the untreated set or last dose of tafamidis in the tafamidis treated set) will be censored.

CCI [Redacted]

[Redacted]

[Redacted]

[Redacted]

- [Redacted]
- [Redacted]
- [Redacted]

CCI [Redacted]

[Redacted]

[Redacted]

[Redacted]

PFIZER CONFIDENTIAL

[Redacted]

CCI

[Redacted]

[Redacted]

[Redacted]

CCI

[Redacted]

[Redacted]

[Redacted]

[Redacted]

[Redacted]

CCI

[Redacted]

[Redacted]

PFIZER CONFIDENTIAL

[Redacted]

CCI [Redacted]

CCI [Redacted]

[Redacted]

[Redacted]

[Redacted]

[Redacted]

[Redacted]

[Redacted]

- [Redacted]
- [Redacted]
- [Redacted]
- [Redacted]

PFIZER CONFIDENTIAL

[Redacted]

CCI [Redacted]

[Redacted]

[Redacted]

[Redacted]

- [Redacted]
- [Redacted]
- [Redacted]
- [Redacted]
- [Redacted]
- [Redacted]

[Redacted]

- [Redacted]
- [Redacted]

[Redacted]

[Redacted]

CCI [Redacted]

[Redacted]

[Redacted]

[Redacted]

CCI [REDACTED]

CCI [REDACTED]

CCI [REDACTED]

[REDACTED]

[REDACTED]

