### **8.2 STATISTICAL ANALYSES**

The baseline visit will be considered as the last available visit on or before the date of sign of informed consent form for the all-enrolled set and the untreated set (as well as any other subgroups corresponding to this untreated set). For the treated set (as well as any other subgroups corresponding to this treated set), the baseline will be considered as the last available value within 3 weeks prior to or 3 weeks after starting tafamidis.

For the subgroup of patients with off-label use, the baseline will be the last available value prior to receiving the first dose of tafamidis 80/61 mg.

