### 8.2.4 Symptoms

The ongoing definitely related symptoms at enrollment/baseline, ongoing possibly related symptoms at enrollment/baseline, and ongoing symptoms at enrollment/baseline unrelated to TTR will be summarized by severity for the following sets: tafamidis treated set by phenotype at enrollment and overall, tafamidis untreated set by phenotype at enrollment and overall, and tafamidis treated set who are either predominantly cardiac or mixed phenotype at enrollment by CCI class at enrollment.

The past definitely related symptoms at enrollment/baseline, past possibly related symptoms at enrollment/baseline, and past symptoms at enrollment/baseline unrelated to TTR will be summarized by severity for the following sets: tafamidis treated set by phenotype at enrollment and overall, tafamidis untreated set by phenotype at enrollment and overall.

Symptoms developed post enrollment/baseline (defined as a symptom with an onset date after the date of enrollment for the untreated set and as a symptom with an onset date after the first dose of tafamidis for the treated subset) will be summarized by severity separately based on whether or not symptoms were definitely related, possibly related, or unrelated to TTR for the following sets: tafamidis treated set by phenotype at enrollment and overall, tafamidis untreated set by phenotype at enrollment and overall, tafamidis treated set who are either predominantly cardiac or mixed phenotype at enrollment by CCI class at enrollment, tafamidis treated set for patients who switched from predominantly cardiac to mixed phenotype, tafamidis treated set for patients who switched from predominantly neurologic to mixed phenotype, tafamidis untreated set for patients who switched from predominantly cardiac to mixed phenotype, tafamidis untreated set for patients who switched from predominantly neurologic to mixed phenotype.

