### Adverse Events & Serious Adverse Events

All adverse events will be coded according to the latest Medical Dictionary for Regulatory Activities (MedDRA) version at the time of analysis.

Adverse events (all causality and treatment-related) will be summarized by severity and starting dose using the tafamidis treated set by phenotype at enrollment and overall, CCI [REDACTED] and either predominantly cardiac or mixed phenotype at enrollment, tafamidis treated set for patients who had severe hepatic impairment at baseline, tafamidis treated set by liver transplantation status (liver transplant prior to first dose of tafamidis/liver transplant after the first dose of tafamidis/no liver transplant).

Separate summaries will be provided for all AEs, treatment related AEs, all SAEs, treatment related SAEs, AEs leading to dose reduction, AEs leading to withdrawal of tafamidis (temporarily or permanently, or delayed) and AEs leading to tafamidis dose interruptions.

Listings will be provided for adverse events corresponding to all enrolled patients and for patients with off-label usage of tafamidis. A separate listing of SAEs will also be provided for tafamidis treated set.

The following AE summary tables will be provided corresponding to some of the important potential risks using the tafamidis treated set.

- For **hepatotoxicity** using the search criteria: MedDRA SMQ (Standardized MedDRA Query) [Broad and narrow] Drug related hepatic disorders – comprehensive search. The derivations and conventions related to the search criteria will follow the programming specifications done in the Periodic Safety Update Report (PSUR) 12 for tafamidis.
- For **reproductive and developmental toxicity and lactation**:
  - MedDRA SMQ (Broad and narrow): Congenital, familial and genetic disorders; Foetal disorders; Neonatal disorders, Neonatal exposures via breast milk.
  - MedDRA Preferred terms (PTs): Exposure during pregnancy, Exposure via father, Foetal exposure during delivery, Foetal exposure during pregnancy, Foetal exposure timing unspecified, Maternal exposure before pregnancy, Maternal exposure during delivery, Maternal exposure during pregnancy, Maternal exposure timing unspecified, Drug exposure before

- pregnancy, Exposure via breastmilk, Maternal drug affecting foetus, Maternal exposure during breastfeeding
- The derivations and conventions related to the search criteria will follow the programming specifications done in the PSUR 12 for tafamidis.

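### Treated-set outputs by phenotype use phenotype at consent even for patients who start tafamidis later, and the SAP 5.4 text and Table 3 classify some patients differently with no rule on which governs

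*SAP*

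**What the plan says.** **Time point.** SAP 5.1: "The enrollment date will be considered as the date when informed consent form (ICF) was signed". For patients not on tafamidis at enrollment who start later, SAP 5.3 takes "All available data from first dose of tafamidis until final treatment discontinuation of tafamidis or end of follow-up in THAOS". SAP 6.2.1: "Survival will be analysed as time from enrollment or first dose of tafamidis, for the untreated and tafamidis treated set respective". For the treated set, SAP 8.2 says "the baseline will be considered as the last available value within 3 weeks prior to or 3 weeks after starting tafamidis", and SAP 8.2.4 counts as a post-baseline symptom "a symptom with an onset date after the first dose of tafamidis for the treated subset". For patients who start tafamidis after joining THAOS, SAP 5.4 (Changes of phenotype) adds that "phenotype treatment baseline will be the most recent phenotype classification prior to first dose".

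The treated-set outputs use a different time point. Adverse events are "summarized by severity and starting dose using the tafamidis treated set by phenotype at enrollment and overall". Symptoms (8.2.4) and survival, exposure, concomitant medications, hospitalization, deaths, ECG and echocardiogram (8.2.6) likewise stratify or select by phenotype at enrollment. The summary table in 8.2.8 says only that outputs are by phenotype and gives no time point.

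**Classification.** SAP 5.4 defines the phenotypes in text, then refers the reader to Table 3 for further detail. It does not say which prevails where the two differ.

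**The concern.** In a treated-set table split by phenotype, the strata should describe patients as they were when treated follow-up began. For later initiators they describe patients at consent, which may be well before. SAP 5.4 also rules out pooling mixed with another phenotype in analysis, and the SAP's change log explains that response to therapy is expected to differ between groups. Yet a patient who became mixed before first dose would be counted on treatment as cardiac or neurologic.

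The classification conflict is a separate defect. Two programmers working from the same SAP could place the same patient in different phenotypes. This reaches the off-label 80/61 mg subgroup, which 5.4 defines by phenotype at first dosing with that dose and which serves a stated objective (SAP 2.2).

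Small strata are the most exposed: subgroups under 10 get listings only, and Kaplan-Meier estimates need at least 5 events.

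**Working it through.** The plan has no hypotheses, sample size or power figure to reproduce, so the check compares sections and enumerates the rules.

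**(a) Time point for a patient who starts tafamidis after consent**

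| Element | Anchor | SAP |
|---|---|---|
| Treated data window | first dose | 5.3 |
| Treated survival time | first dose | 6.2.1 |
| Treated baseline value | within 3 weeks either side of starting | 8.2 |
| Post-baseline symptoms | first dose | 8.2.4 |
| Liver-transplant strata, treated set | first dose | 5.4, 8.2.6 |
| Treatment-baseline phenotype | last classification before first dose | 5.4 |
| Phenotype stratum in nine outputs | consent | 8.2.4, 8.2.6 |

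SAP 5.4 names two changes, cardiac to mixed and neurologic to mixed. Either one, if it falls between consent and first dose, leaves the patient in an out-of-date stratum. The rule "Missing data on prior visit will disqualify re-classification" can only make recorded changes less frequent.

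For the treated ECG sets:
- Cardiac to mixed is still selected, because both phenotypes qualify.
- Neurologic to mixed before first dose is selected only if that counts as having switched. It does not count if switching means a change after treatment baseline.
- A patient asymptomatic or unclassified at consent and first classified as cardiac or mixed before first dose is in no visible treated ECG set. That is 2 x 2 = 4 logical combinations, none of which the documents describe.

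Size (assumption only): share of the treated set in an out-of-date stratum = s x p, where s is the share starting after consent and p the share of those who change phenotype before first dose.
- s = 0.20, p = 0.05: 0.01. s = 0.20, p = 0.20: 0.04.
- s = 0.60, p = 0.05: 0.03. s = 0.60, p = 0.20: 0.12.
- Alternatively, p = 1 - exp(-rt). With r = 0.02 per year and t = 1 year, p = 0.020; with r = 0.10 and t = 5, p = 0.393. That is about 2% to 39% of later initiators.

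**(b) 5.4 text against Table 3**

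mPND is held missing, and the redacted criteria are left out. 'Sign' means rhythm disturbance, heart failure or dyspnea.

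Symptomatic ATTRv: sign yes/no x (no neuro/GI symptom, or ongoing/past x definite/possible/unrelated) = 2 x (1 + 2 x 3) = 14 profiles. Four differ:

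| Profile | Text | Table 3 | Off-label status changes? |
|---|---|---|---|
| No sign, ongoing possibly related | unclassified | neurologic | no |
| No sign, ongoing unrelated | unclassified | neurologic | no |
| Sign, past unrelated only | unclassified | cardiac | yes |
| Sign, ongoing unrelated | mixed | cardiac and mixed | no |

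The first two arise because the text requires definitely related symptoms for the neurologic phenotype, while Table 3 states no relatedness condition. The last two arise because the text bars unrelated neuro/GI symptoms from the cardiac phenotype, while Table 3 names only related or possibly related ones. If the adjacent 'none' cells in that Table 3 row also bar unrelated symptoms, the last two disappear.

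ATTRwt with a sign and a neuro/GI symptom other than erectile dysfunction, constipation or carpal tunnel: ongoing/past x mild/moderate/severe x related/possible/unrelated = 2 x 3 x 3 = 18 profiles. Four differ (past; moderate or severe; related or possibly related: 1 x 2 x 2). The text gives mixed, but they fit no Table 3 row because the mixed row requires ongoing symptoms. Off-label status changes in all four, provided the symptoms resolved before first classification; if they were ongoing then, 5.4 keeps the patient mixed. Past symptoms are collected at baseline (SAP Table 2), so such patients can be recorded.

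These count rule combinations, not patients.

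**The case against.** On the time point, the analyses are descriptive and the stratum is openly labelled. A patient can be in both the untreated and treated sets, and a fixed enrollment label keeps that patient in one stratum across both. That is a sound reason to keep an enrollment version. It does not make the stratum describe phenotype when treated follow-up starts.

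A reader might infer that the SAP defines a treatment-baseline phenotype and never uses it. The documents do not support that. The definition sits in the note to the two become-mixed subgroups, which may use it; the off-label subgroup has its own first-dose rule; and phenotype shift tables listed in the change log, or other redacted parts, may also use it.

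A reader might also infer that ECG and echocardiogram tables will lose cardiac or mixed patients, because tafamidis is used per label (SAP 2.1) and the EU polyneuropathy indication requires symptoms (Protocol 7.1). That inference supports asymptomatic to neurologic, which is not an ECG selection group. Loss of cardiac or mixed patients remains only a logical possibility. It matters less for echocardiogram, which is summarized at baseline only.

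On classification, the wild-type cardiac criteria say symptoms need not be ongoing, and 5.4 assumes phenotype-related symptoms do not truly disappear. The ongoing condition in Table 3 may therefore be a slip. That is plausible, but neither statement is a precedence rule. It would be too strong to say flatly that the off-label count changes for ATTRv patients, since that depends on how the 'none' cells are read.

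No counts show any stratum near the 10-patient or 5-event limits.

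**Conclusion.** Both defects stand, and both should be corrected.

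(a) Nine treated-set outputs place later initiators by phenotype at consent, although their treated data and survival start at first dose. At minimum, patients who go from cardiac or neurologic to mixed in between are reported in the wrong stratum for on-treatment results. Overall columns are unaffected. The range of 1% to 12% of the treated set rests wholly on assumed inputs. For patients already on tafamidis at consent, the treated data window also starts at enrollment, so this mismatch does not arise there.

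(b) The text and Table 3 conflict on ATTRv neurologic and ATTRwt mixed, and on ATTRv cardiac unless the 'none' cells also bar unrelated symptoms. The off-label count can change for an ATTRwt patient with mPND below I or missing whose moderate or severe, related or possibly related symptoms resolved before first classification. It can also change for an ATTRv patient with a cardiac sign and only a past unrelated neuro/GI entry, on that one reading of Table 3. Redacted criteria in the cardiac and neurologic definitions could not be checked.

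**What to change.** (a) In the treated-set outputs for symptoms, survival, exposure, concomitant medications, hospitalization, AE/SAE, deaths, ECG and echocardiogram:
- Use the 5.4 treatment-baseline phenotype for patients who start tafamidis after enrollment.
- Keep enrollment phenotype for patients already on tafamidis at consent, and for the untreated and all-enrolled sets.
- Label the phenotype time point in every table, including demographics and disease characteristics (8.2.2, 8.2.3).
- State for ECG and echocardiogram whether a change before first dose counts as switched.
- Keep an enrollment-phenotype version as a supplement.

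(b) The sponsor must reconcile the 5.4 phenotype text with Table 3 into one mutually exclusive rule set, covering unrelated symptoms for ATTRv cardiac, relatedness for ATTRv neurologic and ongoing status for ATTRwt mixed, and state which governs before patients are classified.

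Cost: SAP wording and a variable the SAP already defines; no new data. The main treated strata will not match earlier reports based on enrollment phenotype, which the supplement covers. The stratifier will use two time points, which labelling makes visible but does not remove.

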5.4	Revised phenotype classification. Added text to clarify the subgroups to be used for safety and other endpoints. Mixed phenotype will not be combined with any other subgroup.	Refine phenotype classification in alignment with clinical presentation. Clarification to highlight that the sample size in a subgroup needs to be at least 10 in order to have sufficient data to provide descriptive statistics. Clinical presentation, natural history of disease and response to therapy is expected to vary between groups. No scientific rationale to present pooled results for mixed combined with any other phenotype.
6.1	CCI [REDACTED]	[REDACTED]
6.3	CCI [REDACTED]	[REDACTED]
7	Update on handling missing values for proportions.	Patients with missing data for a variable will be excluded from the denominator when calculating proportions

		involving observed data for that variable.
8.1	Update on MMRM and Kaplan-Meier analyses. Clarified sample size requirement for descriptive statistics.	Sufficient data not available to conduct MMRM's in order obtain reliable estimates due to small sample size and high drop-out rate. Sample size in a subgroup needs to be at least 10 in order to have sufficient data to provide descriptive statistics, listings will be provided for smaller subgroups. Kaplan-Meier estimates will be provided if the number of events are at least 5.
8.2.1	Disposition data only to be provided for enrolled patients	Disposition data not needed for treated and untreated cohorts.
8.2.2, 8.2.3, 8.2.4	Add additional variables to be summarized in demographics and disease characteristics table Additional summary on frequency distribution of TTR variants for all enrolled patients. Modification of the text related to symptoms developing post enrolment/baseline.	Demographics: additional variables added – duration of ATTR symptoms at enrollment, time from symptom onset to diagnosis, age at onset of symptoms, follow-up time. Disease characteristics: additional variables added – BMI, mBMI, CCI [REDACTED] [REDACTED] systolic BP, diastolic BP, LV septum, LV ejection fraction, CCI [REDACTED] [REDACTED] Heart failure, abnormal ECG, Atrial fibrillation/flutter,

PFIZER CONFIDENTIAL

		
participation frequency (%) in tafamidis trial and non-tafamidis trial.
 
As per the nature of the disease, the definition of “new” symptoms is vague and are actually pre-existing symptoms associated with the disease that could onset after enrolment/baseline.

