## 5.2 TAFAMIDIS UNTREATED

The tafamidis untreated set will include the following:

- All available data from patients who have been enrolled in THAOS, signed the informed consent and who have not received tafamidis during the THAOS study.
- All available data before receiving the first dose of tafamidis while in THAOS, for those patients who were not on tafamidis during or after initial enrollment in THAOS but then started receiving tafamidis post enrollment.

Note: Available data after a patient discontinues treatment with tafamidis will be excluded (See Figure 1)

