### 8.2.1 Disposition

Disposition status, along with reasons for discontinuation (from treatment as well as study) will be summarized by number and percentage of patients for the all enrolled patients.

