8.2.8 Summary of Analyses

Data	All enrolled	Untreated overall & by phenotype	Untreated predominantly neurologic/mixed	Untreated predominantly cardiac/mixed	Treated Overall and by phenotype	Treated predominantly neurologic/mixed	Treated predominantly cardiac/mixed	Treated by starting dose	[REDACTED]	[REDACTED]	Treated severe hepatic impaired at baseline	Patients not on tafamidis at the time of enrollment with a liver transplant prior to enrollment on THAOS	Patients not on tafamidis at the time of enrollment with a liver transplant after enrollment on THAOS	Patients not on tafamidis at the time of enrollment with no liver transplant	Treated with liver transplant prior to first dose of tafamidis in the study	Treated with liver transplant after first dose of tafamidis in the study	Treated with no liver transplant either prior to first dose of after first of tafamidis in the study	Treated with off-label usage	Untreated predominantly neurologic who become mixed	Untreated predominantly cardiac who become mixed	Treated predominantly neurologic who become mixed	Treated predominantly cardiac who become mixed
Disposition	x	x			x																	
Demography	x	x			x																	
Disease Characteristics	x	x			x																	
Misdiagnoses	x	x			x																	
Ongoing symptoms by A.T.T.R		x			x				x													
relatedness (definite/possibly related/unrelated)																						
Past symptoms by A.T.T.R		x			x																	
relatedness (definite/possibly related/unrelated)																						
New symptoms by A.T.T.R		x			x																	

PFIZER CONFIDENTIAL

CCI				x			x		x			x							x			x	
				x			x		x														
			x			x						x	x	x							x		x
Survival		x			x					x	x	x	x	x	x	x	x						
Exposure to Tafamidis					x			x		x	x				x	x	x						
Concomitant medications		x			x																		
Hospitalizations		x			x					x													
AE/SAE					x			x		x	x				x	x	x	x					
Death	x	x			x					x	x	x	x	x	x	x	x						
Labs – baseline and change from baseline		x			x			x															
Hy's Law					x			x															

Blood pressure – baseline and change from baseline	x	x			x															
ECG				x			x			x								x		x
ECHO				x			x			x								x		x
CCI		x			x															
[REDACTED]			x			x														
[REDACTED]			x			x														
[REDACTED]			x			x														
[REDACTED]				x			x		x									x		x
[REDACTED]				x			x													
Transplant		x			x															
[REDACTED]		x			x															

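### Permanent AE-related stopping of tafamidis cannot be read from the planned AE tables, and treatment discontinuation is expressed as a percentage of all enrolled patients

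*SAP*

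**What the plan says.** **AE tables.** SAP 8.2.6 (Adverse Events & Serious Adverse Events) lists, among its separate summaries, "AEs leading to withdrawal of tafamidis (temporarily or permanently, or delayed) and AEs leading to tafamidis dose interruptions". AEs are "summarized by severity and starting dose using the tafamidis treated set by phenotype at enrollment and overall", so the base is treated patients. The SAP does not define temporary withdrawal, delay or interruption, and lists no summary of AEs that ended tafamidis for good.

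**Disposition.** SAP 8.2.1 says that "reasons for discontinuation (from treatment as well as study) will be summarized by number and percentage of patients for the all enrolled patients". SAP 5.2 shows that enrolled patients include those who "signed the informed consent and who have not received tafamidis during the THAOS study". The change log for the current SAP version (Section 1, Amendment 2) confirms that this was intended: "Disposition data only to be provided for enrolled patients". The analysis grid in SAP 8.2.8 nevertheless marks the Disposition row under the untreated column and under "Treated Overall and by phenotype".

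**Related text.** The note to Figure 1 in SAP 5.3 takes discontinuation to mean the final one, but for building the analysis sets. The Amendment 1 rationale for 5.3 acknowledges that a patient may stop more than once. SAP Table 2 lists a tafamidis log with dose, start dates and stop dates. The Amendment 2 rationale for 8.2.6 says that the CRF holds only limited information on stopping.

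**The concern.** The survey is a post-authorisation safety study and an EMA commitment (Protocol 7.3; SAP 2), and summarising safety in tafamidis-treated patients is one of its objectives (Protocol 8; SAP 2.2). In that setting a reader will look for the share of treated patients who stopped for good, and the share who did so because of an adverse event. Two outputs come close, and neither clearly supplies it. The AE summary mixes patients who resumed with patients who did not. The disposition percentage, on the wording of 8.2.1, is taken over a set in which some patients had no treatment to discontinue.

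The figure also matters for survival. SAP 6.2.1 censors living treated patients at their last dose. To judge whether that censoring is related to prognosis, a reader needs to know how many treated patients stopped for good, and why.

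**Working it through.** The plan states no sample size, treated share or stopping rate, and all its analyses are descriptive (SAP 4), so there is no figure to reproduce. The check compares the texts and then uses simple arithmetic on assumed values.

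**1. The two outputs side by side**

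| | AE summary (8.2.6) | Disposition (8.2.1) |
|---|---|---|
| What is counted | permanent, temporary and delayed stops together | treatment discontinuation, with reasons; not stated to be final |
| Base | tafamidis treated set | all enrolled (text); also treated and untreated sets (8.2.8 grid) |
| Shows permanent AE-related stopping? | no | only if the reasons include adverse events and the final stop is used; neither is stated |

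Numerator and base both differ, so one output cannot stand in for the other.

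**2. Dilution from the all-enrolled base**

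Let *f* be the share of enrolled patients ever treated and *p* the proportion of treated patients who stop. Both are assumptions.

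Percentage of all enrolled = *f* × *p*

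| *p* among treated | *f* = 0.3 | *f* = 0.5 | *f* = 0.7 |
|---|---|---|---|
| 10% | 3% | 5% | 7% |
| 20% | 6% | 10% | 14% |

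Whatever *p* is, the multiplier equals the treated share. Using treated patients as denominator restores 10% or 20%.

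**3. Pooling in the AE withdrawal summary**

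Let *a* be the proportion of treated patients with a permanent AE-related stop and *t* the proportion with only a temporary or delayed one. Both are assumptions.

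Pooled figure = *a* + *t*; ratio to permanent = (*a* + *t*) / *a*

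| *a* | *t* = 2% | *t* = 5% | *t* = 10% |
|---|---|---|---|
| 5% | 7% (1.4 times) | 10% (2 times) | 15% (3 times) |
| 2% | 4% (2 times) | 7% (3.5 times) | 12% (6 times) |

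**4. Possible overlap with the interruption summary**

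If every temporary or delayed stop also counts as an interruption, the two tables together show *a* + 2*t*. With *a* = 5% and *t* = 5% that is 15%, against 10% distinct patients. If the coding keeps the two apart, there is no double counting. The SAP does not say which applies.

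**The case against.** Several points on the other side have weight.

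- **The composite is openly labelled.** The line in 8.2.6 says that it covers temporary, permanent and delayed stops. A reader might infer that the AE figure is wrong or too high. The documents do not support that: it is a different quantity from permanent discontinuation, correctly described. What stands is that the permanent part cannot be separated out.
- **The two AE tables are not duplicates.** A reader might infer that the withdrawal table repeats the interruption table. It does not, because it also holds permanent stops. Since the documents do not show how action on tafamidis is coded, only a possible overlap with an undefined boundary can be claimed.
- **The denominator might turn out right in practice.** SAP 7 and 8.1 base proportions on non-missing values unless otherwise specified, so never-treated patients could drop out if they carry no treatment-discontinuation value. The 8.2.8 grid also points to a treated-set table. But 8.2.1 specifies all enrolled, Amendment 2 shows that this was deliberate, and nothing says that never-treated patients are left out for this item. The grid looks as if it was not updated.
- **Counts will still be available.** 8.2.1 gives numbers as well as percentages, and other tables will show the treated total, so a reader could recompute a percentage. This rules out saying that the outputs can never be reconciled. It does not settle whether the count refers to final discontinuation.
- **The CRF may not support the split.** Amendment 2 dropped the summary of dose increase, decrease and stopping because the CRF holds limited information, and the tafamidis log in Table 2 lists no stop reason. This is a real constraint on the AE part. However, the planned withdrawal summary already presupposes some link from an AE to a stop, and the log dates can show whether a restart followed.

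**Conclusion.** The concern holds as a defect of reporting. Permanent AE-related stopping of tafamidis cannot be read from the AE tables as planned. The treatment-discontinuation percentage, if 8.2.1 is followed as written, is diluted by the treated share, and 8.2.8 contradicts 8.2.1 on which sets receive a disposition table.

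The size is not known. Over assumed treated shares of 30% to 70% the multiplier is 0.3 to 0.7. Over the assumed stopping rates the pooled AE figure is 1.4 to 6 times the permanent one. The two effects run in opposite directions and act on different outputs. These values show how the plan behaves and are not estimates for this survey.

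The plan should be changed here, because the figure is a basic one for a safety study and the change is small. No hypothesis test is affected, and the documents do not show that any reported result will be false.

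**What to change.** 1. **SAP 8.2.1.** Keep study discontinuation on all enrolled patients. Report final tafamidis discontinuation and its reasons with treated patients as denominator, and say that the final stop is meant, as in the note to Figure 1.
2. **SAP 8.2.8.** Bring the Disposition row into line with the revised 8.2.1.
3. **SAP 8.2.6.** Replace the pooled withdrawal summary and the separate interruption summary with two mutually exclusive reporting categories: *AEs leading to permanent discontinuation of tafamidis* and *AEs leading to temporary interruption or delay*. Use the AE data that already feed the planned summaries, and the tafamidis log start and stop dates to identify restarts. State how a stop still open at the end of follow-up is classified.
4. **Feasibility.** Before fixing the categories, confirm what the CRF records about action taken on tafamidis. If the AE link is too weak for the split, say so in the SAP and rely on the treated-set table from step 1.

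The cost is a few sentences, some table-shell edits and the CRF check. No new data collection is proposed, and no clinical rule is changed.
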